16.1 Responsibilities of Sponsor.....	32

16.2 Responsibilities of Medical Device Clinical Research Institutions	33
16.3 Responsibilities of Investigators	34
17 Miscellaneous Issues to be Clarified.....	34
17.1 Finance and Insurance.....	34
17.2 Agreement on Study Result Publication	34
Investigator Statement.....	35
References	36
List of Figures	
Figure 2-1 FRED System Setup.....	15
Figure 2-2 FRED Implant Nomenclature.....	15

List of Tables

Table2-1 List of Specifications and Models	15
Table 4-1 Raymond-Roy Classification Standards	21
Table 4-2 Modified Rankin Scale (mRS).....	22

List of Abbreviations

Abbreviation	Full Term
AE	Adverse Event
APTT	Activated Partial Thromboplastin Time
CEC	Clinical Event Committee
CI	Confidence Interval
CRA	Clinical Research Associates
CRO	Contract Research Organization
CTA	Computed Tomography Angiography
CS	Clinically Significant
CSR	Clinical Study Report
DSA	Digital Subtraction Angiography
EC	Ethics Committee
eCRF	electronic Case Report Form
EDC	Electronic Data Capture
FD	Flow Diverter
FIB	Fibrinogen
FRED	Flow Re-Direction Endoluminal Device
GCP	Good Clinical Practice
IA	Intracranial Aneurysms
ICF	Informed Consent Form
IFU	Instructions For Use
MRA	Magnetic Resonance Angiography
mRS	modified Rankin Scale
NMPA	National Medical Products Administration
OKM	O'Kelly-Marotta
PD	Protocol Deviation
PED	Pipeline Embolization Device
PI	Principal Investigator
PT	Prothrombin Time
SAE	Serious Adverse Event
SAH	Subarachnoid Hemorrhage
SAP	Statistical Analysis Plan
SAR	Statistical Analysis Report
SDV	Source Data Verification
TEG	thromboelastographic
TT	Thrombin Time
UIA	Unruptured Intracranial Aneurysms

Protocol Synopsis

Sponsor	MicroVention, Inc.
Study Title	A retrospective, post-market clinical study of the flow re-direction endoluminal device system in the treatment of intracranial aneurysms.
Protocol No.	CL1106094
Version/Date	Version A, 2025-01-21
Study Objective	To evaluate the long-term safety and efficacy of Flow Re-Direction Endoluminal Device System (FRED) in the treatment of intracranial aneurysms in the post-market environment
Study Design	Post-market, retrospective, multi-center, observational clinical study
Study Population	Patient who has implanted at least one observational device in China mainland.
Observational Device	Flow Re-Direction Endoluminal Device System (FRED)
Study Duration	About 36 months.
Inclusion and Exclusion Criteria	
Inclusion Criteria: A patient is eligible for inclusion in the study if he/she meets all the following
 
1) People in China mainland who have been treated with FRED.2) The patients for whom clinical data are available. 
Exclusion Criteria: Patients who met the inclusion criteria at all time points were required to be included in the study. Therefore, no specific exclusion criteria were set.

Data Collection	
Demographic data and other baseline characteristics 人口统计学数据和其他基线特征
 
• Birth date• Sex: Male/ Female• History of smoking and drinking: Yes/No• Ethnicity: Han/ another ethnicity• Diagnosis• Modified Rankin Scale (mRS)• Physical Examination: Neurological physical examination.

	
Medical History
 
Past medical history: including current medical conditions (high blood pressure, diabetes, etc.), history of cranial and neurological related surgeries, hemorrhagic stroke. 
Information of Procedure
 
Before Procedure
Aneurysm Information: aneurysm location (left/right, C2 petrous segment - C7 terminus), aneurysm size (aneurysm maximum diameter, aneurysm neck, width, dome to neck ratio) and morphology (saccular aneurysm, dissecting aneurysm, fusiform aneurysm), ruptured / unruptured/ recurrent and the information of the parent artery (diameter, stenosis) [Base Computed Tomography Angiography(CTA)].laboratory examination (clinically significant abnormal results only).Information of antiplatelet function test result: platelet aggregation test/ Thromboelastographic (TEG);Information of anti-coagulation and anti-platelet medication: drug name, dosage and frequency of administration.Using information of device
Microcatheter: product name, model, sizeCoil usage: Yes/No and numberBalloon: Yes/No and numberFRED: number, model, lot numberInformation of procedure
Puncture position (femoral artery/radial artery, left/right)Re-sheathing performance: whether re-sheathing after release, re-sheathing times, re-sheathing success or notImaging results of immediate post-operation: stent fully cover the aneurysm neck, good wall apposition, parent artery perfusion, retention of contrast media.Procedure complication: Complications of arterial puncture including pain, local bleeding, or injury to the artery, or adjacent nerves. Dissection or perforation of the parent artery, Rupture or perforation of the aneurysm, Vasospasm, Stent thrombosis, et al.Information of follow up
Imaging Evaluation of a Target Aneurysm: Digital Subtraction Angiography (DSA), Magnetic Resonance Angiography (MRA), CTA
--	--

	
can be accepted.
 
- Treatment-related hospitalization information or adverse event information: Stroke, Death, Adverse Event, Serious Adverse Event.
Endpoint	
Safety Endpoints[Adjudicated by Clinical Event Committee (CEC)]
 
1) stroke Rate2) All-cause Mortality3) Lesion-Related Symptoms or Signs Rate4) Lesion-Related Complication Rate (Immediate post-procedure)5) Adverse Event (AE), Serious Adverse Event (SAE)
Statistical Analysis Method	
Efficacy Endpoints
 
1) Imaging Evaluation of Target Aneurysm [O'Kelly-Marotta(OKM) Grade]2) Adequate Occlusion Rate of Target Aneurysm (Base Raymond-Roy Grade)3) Technical Success rate (Immediate post-procedure)4) Re-sheathing Performance (Immediate post-procedure)5) Modified Rankin Scale (mRS) Change from Baseline 
Sample Size Estimation This study is an observational study that does not involve statistical hypotheses. Therefore, the plan is to collect data on as many patients as possible who received FRED treatment for intracranial aneurysms in China from May 2023 to May 2027, and as such, there is no specific sample size estimation.
 
Statistical Analysis Datasets The dataset will consist of all study patients who meet the inclusion and exclusion criteria.
 
General Principles of Statistical Analysis Detailed information on statistical analyses will be described in a separate Statistical Analysis Plan (SAP), with the final version of the SAP to be completed prior to database lock. The statistical analysis will be performed for this study using SAS® (version 9.4 or

	
higher).
 
This study is observational in design and does not involve statistical inference or hypothesis testing. Descriptive statistics for continuous variables will include the number of observations, mean, standard deviation, median, minimum, maximum values, and quartiles (Q1, Q3).
 
Baseline Analysis
 
Demographic, clinical characteristics, and treatment information of the patients including age, gender, medical history, physical examination, laboratory, surgical information, are statistically described. The methodology will adhere to standard principles.
 
Endpoint analyses:
 
This study is observational and does not involve statistical inference.
 
Descriptive analyses will be conducted on safety and efficacy endpoints. For binary endpoints, counts and percentages will be provided, with 95% confidence intervals (CIs) estimated using the exact binomial method. Survival endpoints will be assessed using the Kaplan-Meier method to estimate survival probabilities and calculate the corresponding 95% CIs, accounting for censored data. Continuous endpoints will be summarized with counts, means, medians, standard deviations, minimums, maximums, and interquartile ranges, along with their 95% CIs.
 
Stage Analysis
 
According to the requirements of National Medical Products Administration (NMPA), the collected data will be divided according to the following schedule, and the statistics and analysis of clinical data during the corresponding collection period will be completed once a year:
 
- During May 2023 to May 2025- During June 2025 to May 2026- During June 2026 to May 2027
--	--

1 Sponsor Information

1.1 Sponsor Name

MicroVention, Inc

2.1 Design Background

2.1.1 Disease Explanation

Intracranial Aneurysms (IAs) are abnormal bulges that caused by localized vascular wall damage in intracranial arteries. The prevalence of IAs in the general population is estimated to be approximately 3%-5%. Once an aneurysm ruptures, leading to Subarachnoid Hemorrhage (SAH), the mortality rate can reach up to 40%^[1, 2].

The symptoms of IA can manifest as neurological dysfunction caused by mass effect or thrombosis, but the most common clinical presentation is SAH, typically presents with a sudden, severe headache and may be accompanied by transient loss of consciousness, vomiting, neck pain or stiffness^[3]. Most Unruptured Intracranial Aneurysms (UIA) lack specific clinical symptoms and are often discovered incidentally, with only a few detected due to symptoms such as headaches or ptosis. Some patients with unruptured aneurysms may present with symptom, including visual disturbances (due to compression of the optic nerve), cranial nerve palsies (especially third nerve palsy), corticospinal tract dysfunction, and facial pains^[4].

2.1.2 Treatment Options

The main principle of treating IAs is to exclude the aneurysm from the circulation to prevent rupture or re-rupture. There are two main treatment strategies: surgical clipping via craniotomy and endovascular treatment. The ideal endovascular treatment shall achieve complete aneurysm occlusion while preserving the parent artery. With this technique, a microcatheter is introduced via a transfemoral approach and manipulated into the cerebral aneurysm under fluoroscopic guidance. Following catheterization of the aneurysm, multiple detachable coils are placed within the aneurysm fundus, inducing aneurysm thrombosis, and again isolating the aneurysm fundus from the parent artery circulation^[1].

Traditional endovascular techniques focus on intra-aneurysmal embolization, with primary methods including simple coil embolization and stent-assisted coiling. However, the effectiveness of these techniques is often constrained by the morphological characteristics of the aneurysm. Wide-neck aneurysms (defined as a neck width ≥ 4 mm or a dome-to-neck ratio < 2) are particularly challenging to treat. By utilizing coils for physical packing of the aneurysmal sac, the lack of effective support at the aneurysm neck often results in coil prolapse into the parent artery. This can lead to compromised blood flow to distal regions supplied by the parent artery, causing neurological deficits and severely affecting the patient's clinical outcomes.

Flow Diverter (FD) devices are developed based on reconstructing the parent artery's lumen. FDs are designed with a denser mesh compared to conventional intracranial stents. By covering the aneurysm neck, these stents redirect blood flow away from the aneurysm, promoting intra-aneurysmal flow stagnation and subsequent thrombosis formation. Currently, FDs are primarily used for the treatment of wide-neck aneurysms^[1].

At present, there are two major flow diverter devices in use. The first is the SILK, developed by BALT. The SILK device consists of a stent made from 48 braided nitinol and platinum alloy wires. The stent

delivery system comprises both the stent and a microcatheter, and the stent can be retrieved before 90% of deployment. SILK has been approved for marketing in the European Union. The second device is the Pipeline Embolization Device (PED), manufactured by Medtronic in the United States, which is similarly composed of 48 braided nitinol-platinum-iridium alloy wires. Its basic components are like those of the SILK device. PED has been approved for use in the EU, by the U.S. FDA, and by China's NMPA.

2.1.3 Observational Device

The design of the observational device Flow Re-Direction Endoluminal Device (FRED) system is comparable to other approved devices with the same or similar indications. FRED has been approved for use by the U.S. FDA on December 16, 2019, and received market approval from China's NMPA on May 12, 2022, with registration number 国械注进 20223130235. The self-expanding nitinol stent is the implantable portion of the Flow Re-Direction Endoluminal Device (FRED) system. The stent consists of two integrated nitinol braided inner and outer layers with the outer layer containing flare ends. The inner layer is of lower porosity, braided in a 36-wire format using 36 individual wires (FRED 2.5 mm and 3.0 mm), or 48 wire formats using 48 individual wires (FRED 3.5 mm to 5.5 mm). The outer stent layer is of higher porosity, braided in a 16-wire format using a single wire that is passed around a mandrel 16 times. Two radiopaque wires are inter-woven between the outer and inner layers along the length of the inner layer implant in a helix configuration. There are four radiopaque markers at each end of the stent.

The FRED system features a dual-layer stent design. The inner stent is similar in design to the SILK and PED devices, while the outer stent is designed with similar materials and structure to coil-assist stents currently in use, such as the LVIS™ (MicroVention), the Neuroform™ Stent System (Boston Scientific) and the Enterprise™ Vascular Reconstruction Device (Johnson & Johnson).

This clinical study is conducted in accordance with NMPA requirements to evaluate the long-term follow-up safety information of FRED following its market release.

2.2 Basic Composition of the Observational Device

2.2.1 Structural Composition

The FRED System [see **Figure 2-1** and **Figure 2-2**] consists of a self-expanding nickel-titanium implant and a delivery system. The implant is designed to expand to a pre-determined diameter when released from the delivery system. The implant features integrated dual layer coverage designed to focus mainly on the neck of an intracranial aneurysm. The implant has distal and proximal markers on its ends and interweaved helical marker strands delineating the inner working length of the implant to provide fluoroscopic visibility.

The FRED System is packaged sterile as a single unit with the implant, introducer sheath and a detachable delivery pusher. It is available in 7 different implant diameters ranging from 2.5 mm to 5.5 mm and in different implant lengths ranging from 13 mm to 45 mm. The FRED System 2.5 mm and 3.0 mm implants are compatible with the Headway 21 Microcatheter (FRED-21 System). The FRED System 3.5 mm to 5.5 mm implants are compatible with the Headway 27 Microcatheter (FRED-27 System).

[figure not shown]

Figure 2-1 FRED System Setup

[figure not shown]

Figure 2-2 FRED Implant Nomenclature

Table 2-1 List of Specifications and Models

Device	Outer Diameter (mm)	Total Lengths (mm)	Working Lengths (mm)
FRED System FRED	2.5	13~30	8~26
	3.0	13~32	9~27
	3.5	13、17、22、31、40	7、11、16、24、36
	4.0	13、18、23、32、44	7、12、17、26、38
	4.5	15、20、25、34、45	8、13、18、28、39
	5.0	15、21、26、36	9、14、19、29
	5.5	22、32	14、26

Specifications and Models of Product(s) to be Used in Combination

Microcatheter	Lengths	Minimum inner diameter of guide duct	Recommended Guide
Headway 17	150 cm	0.056 inch / 1.42 mm	≤ 0.014 inch / ≤ 0.36 mm
Headway 21	150 cm	0.056 inch / 1.42 mm	≤ 0.018 inch / ≤ 0.46 mm
Headway 27	150 cm	0.056 inch / 1.42 mm	≤ 0.018 inch / ≤ 0.46 mm

2.2.2 Principle of Operation and Mode of Action

The observation device is a flow diverter (FD) designed for permanent implantation into the lumen of the aneurysm or vascular dissection to carry the aneurysm. The approach site is usually an angiography-guided femoral artery. Neurovascular access is obtained according to standard endovascular maneuvers. This can be achieved by navigating the guidewire to the location of the aneurysm neck or to the target location, and then the microcatheter is navigated through the guidewire. After removing the guidewire, select the appropriate size flow guide according to the instructions for use (IFU). The instrument is assembled inside a coil and placed in a sterile area. The device (implant/delivery pusher/introduction sheath) is removed from the coil as a whole. The blood flow guide was inspected and prepared according to the IFU. Follow the "Instructions for Use" in the IFU to push the FRED implant into the microcatheter by pushing the delivery guidewire. By delivering a guidewire, the implant can advance further through the microcatheter until it reaches the distal tip of the microcatheter, but not beyond the microcatheter tip (proximal fluorescent labeling on the FRED delivery system can aid in this process). At this point, fluoroscopy must begin. While the implant remains within the microcatheter, it is positioned and deployed by aligning its distal radiopaque end marker. Once the position has been determined under fluoroscopy, the microcatheter is retracted and the delivery guidewire is advanced to allow the FRED implant to unfold in the aneurysm neck. If the implant is not fully deployed, it can be retracted and repositioned if necessary. Once deployed, the implant expands and clings to the wall of the blood vessel and across the neck of the aneurysm.

2.3 Scope of Application and Relevant Information

2.3.1 Indication(s)

The FRED System is indicated for use in the internal carotid artery from the petrous segment to the terminus for the endovascular treatment of adult patients (22 years of age or older) with wide-necked (neck width ≥ 4 mm or dome-to-neck ratio < 2) saccular or fusiform intracranial aneurysms arising from a parent vessel with a diameter ≥ 2.0 mm and ≤ 5.0 mm.

2.3.2 Applicable Sites

Internal carotid artery from the petrous segment to the terminus.

2.3.3 Mode and Duration of Contact with Human Body

Prolonged and continuous blood contact (>30 days).

2.3.4 Applicable Disease Stage and Intensity

Intracranial aneurysms.

2.3.5 Condition of Use

Sterile medical environment.

2.3.6 Reuse

Sterile delivery, single use only.

2.3.7 Directions for Use

Please refer to Instructions for Use (IFU).

2.3.8 Contraindications

Use of the FRED System is contraindicated under these circumstances:

- Patients in whom anticoagulant, anti-platelet therapy, or thrombolytic drugs are contraindicated.
- Patients with known hypersensitivity to metal such as nickel-titanium and metal jewelry.
- Patients with anatomy that does not permit passage or deployment of the FRED System.
- Patients with an active bacterial infection.
- Patients with a pre-existing stent in place at the target aneurysm.
- Patients in whom the parent vessel size does not fall within the indicated range.
- Patients who have not received dual anti-platelet agents prior to the procedure.

2.3.9 Precautions and Warnings:

Please refer to Instructions for Use (IFU).

3 Clinical Study Objective

To evaluate the long-term safety and efficacy of post-marketing of Flow Re-Direction Endoluminal Device System (FRED) in the treatment of intracranial aneurysms.

4 Clinical Study Design

4.1 Overall Design and Selection Rationale

This is a post-market, retrospective, multi-center, observational clinical study.

The study plans to enroll patients who meet the eligibility criteria and have received at least one implantation of the observational device between May 2023 and May 2027. The retrospective data will be collected on baseline characteristics, information of procedure, and safety and efficacy endpoint to assess the safety and efficacy of FRED in the Chinese population. The efficacy endpoints include technical success rates and re-sheathing performance, the complete occlusion rate, and modified Rankin Scale (mRS) change from baseline. The safety endpoints include the rates of stroke, mortality, lesion-related symptoms or signs rate, lesion-related complication rate, adverse event, serious adverse event.

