4.2.2 Exclusion Criteria

Patients who met the inclusion criteria at all time points were required to be included in the study. Therefore, no specific exclusion criteria were set.

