4.4.2 Efficacy Endpoint

(1) Imaging Evaluation of a Target Aneurysm (O' Kelly-Marotta, (OKM))

Definition: Based on the evaluation of imaging results, the treatment of aneurysms was classified according to the following criteria. Digital Subtraction Angiography (DSA), Magnetic Resonance Angiography (MRA), or Computed Tomography Angiography (CTA) are acceptable, and it is recommended base CTA. The purpose of imaging follow-up information collection is to observe the effect of on the long-term closure of the aneurysm after treatment. Complete closure of the aneurysm would be associated with increased safety.

- No filling
- Entry remnant (<5%)
- Subtotal filling (5%~95%)
- Total filling (>95%)

The observational device with the blood flow and the aneurysm gradually closes. The evaluation results of different follow-up nodes were counted, and the time interval between the date of surgery and the aneurysm occlusion is collected.

(2) Adequate Occlusion Rate of Target Aneurysm

Definition: Adequate Occlusion is defined as Raymond-Roy Grade I or Grade II on imaging evaluation of the target aneurysm ^[5]. If the Raymond-Roy grade reaches Grade I at any evaluation point, no further imaging information will be collected. Imaging results obtained via Digital Subtraction Angiography (DSA), Magnetic Resonance Angiography (MRA), or Computed Tomography Angiography (CTA) is acceptable. The imaging results will be evaluated following the routine procedures of the clinical research institution. The post-procedure recanalization of the aneurysm is graded according to the following classification. Please refer to **Error! Reference source not found.** for Raymond-Roy Classification Standards.

Table 4-1 Raymond-Roy Classification Standards

Grade	Description
Grade I	Complete occlusion (no contrast filling in the aneurysm sac or neck)
Grade II	Neck remnant (contrast filling in the aneurysm neck but not the sac)
Grade III	Residual sac (contrast filling in the aneurysm sac)

Occlusion Rate of Target Aneurysm refers to the proportion of patients judged to be Grade 1 or Grade 2 in the total number of patients.

(3) Technical Success Rate

Definition: Technical success is defined as successful stent placement and meet following criteria:

- Stent fully cover the aneurysm neck
- Good wall apposition
- Perfusion of the parent artery
- Retention of contrast agent within the aneurysm.

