The technical success rate refers to the proportion of technically successful patients in the total number of patients.

(4) Re-sheathing performance

Definition: During procedure, the observational device can be retrieved / re-sheathed into the microcatheter and re-deployed at the desired target location or removed completely from the patient. But it must not be re-deployed more than three times. Re-sheath performance refers to the retrieving and re-deploying of observational device recorded during the procedure. Information such as the number of recoveries and the number of re-sheathings, the success rate of re-opening and other information are recorded to evaluate the re-sheath performance of the observational device.

(5) Modified Rankin Scale (mRS) Change from Baseline

Definition: At different follow-up, the modified Rankin score changed from the baseline.

The modified Rankin (mRS) score was used to evaluate the improvement of neurological function. The modified Rankin score assesses the ability to live independently in patients with Neurological disease [6]. There are 7 levels of this score, 0 points represent no symptoms of disability, higher scores mean worse prognosis of patients, and 6 points represent death, See the table below for detailed scores.

Table 4-2 Modified Rankin Scale (mRS)

Score	Patient Condition
0	No symptoms of disability
1	Minor symptoms but no significant deficits; capable of all activities and work
2	Mild disability; unable to participate fully in previous activities but can live independently
3	Moderate disability; requires assistance but can walk independently
4	Moderate to severe disability; unable to walk independently, cannot live alone, requires some care
5	Severe disability; bedridden, incontinent, requires constant care
6	Death

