5.1 Sample Size Estimation

Not applicable.

This study is an observational study that does not involve statistical hypotheses. Therefore, the plan is to collect data on as many patients as possible who received FRED treatment for intracranial aneurysms in China from May 2023 to May 2027, and as such, there is no specific sample size

estimation.

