5.2 Statistical Analysis Datasets

The dataset will consist of all study patients who meet the inclusion and exclusion criteria.

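### The population is defined both by implantation and by treatment; if implantation governs, attempts that left no FRED in place drop out and technical success is overstated

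*Protocol*

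**What the plan says.** The protocol describes who is in the study in two ways.

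**Implantation required**
- Synopsis, Study Population row: "Patient who has implanted at least one observational device in China mainland".
- Section 4.1: patients who satisfy the eligibility criteria and who "have received at least one implantation of the observational device between May 2023 and May 2027". The word *and* makes implantation an additional condition.

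**Treatment only**
- Inclusion criterion 1, worded identically in the synopsis and in 4.2.1: "People in China mainland who have been treated with FRED".
- Section 5.1: "as many patients as possible who received FRED treatment for intracranial aneurysms in China from May 2023 to May 2027".

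Two other sections bear on this without settling it. Section 4.2.2 sets no exclusions and states: "Patients who met the inclusion criteria at all time points were required to be included in the study". Section 5.2 refers back to the criteria: "The dataset will consist of all study patients who meet the inclusion and exclusion criteria".

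Technical success is defined in 4.4.2(3). For the numerator, "Technical success is defined as successful stent placement and meet following criteria"; four imaging conditions follow. For the denominator, "The technical success rate refers to the proportion of technically successful patients in the total number of patients". Section 4.4.2(4) recognises that a device can be taken out of the patient altogether during the procedure. The protocol does not say whether a patient who leaves the procedure with no FRED belongs to the study.

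**The concern.** Successful placement is the first component of technical success. A population restricted to patients with an implant has already been selected on that component, so a procedure that ended with no FRED in place cannot appear as a failure.

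This matters by the protocol's own standards. Section 4.4.3 names technical success as an indicator the regulator requires. Section 4.6 relies on enrolling every eligible patient as its protection against selection bias. The choice also has to be made before data are collected, because a SAP cannot restore procedures that were never abstracted. If sites read *treated* differently, the denominator may differ from site to site.

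Re-sheathing experience and procedural complications in failed attempts would be lost in the same way. Occlusion, stroke and mortality also use all patients as denominator and so depend on the same wording, but the direction of any effect on them cannot be derived from the protocol.

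**Working it through.** **Reading the text**

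There are three ways to apply it.

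1. The condition in 4.1 and the Study Population row governs. Attempts left with no FRED are not enrolled.
2. The inclusion criteria govern and *treated* means *implanted*. The result is the same as in 1.
3. The inclusion criteria govern and *treated* includes attempts. These patients are enrolled and count as technical failures, and no bias arises. Section 4.1 and the Study Population row are then wrong, and 4.2.2 leaves no room for their extra condition.

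A patient who has one device removed and another FRED implanted is included under all three.

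**Size under readings 1 and 2**

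The protocol gives no sample size, expected success rate or frequency of attempts without an implant, so it has no figure to reproduce. Both inputs are assumptions:
- p = technical success rate among implanted patients, taken as 90–98%;
- f = share of attempted patients left with no FRED, taken as 0–5%.

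For N attempted patients:
- enrolled = (1 − f)N
- successes = p(1 − f)N, since an attempt with no implant cannot succeed by definition
- reported rate = p(1 − f)N / [(1 − f)N] = p
- rate among all attempts = p(1 − f)N / N = p(1 − f)
- overstatement = p − p(1 − f) = p × f

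Overstatement in percentage points:

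| f | p = 90% | p = 95% | p = 98% |
|---|---|---|---|
| 0% | 0 | 0 | 0 |
| 0.5% | 0.45 | 0.475 | 0.49 |
| 1% | 0.90 | 0.95 | 0.98 |
| 2% | 1.80 | 1.90 | 1.96 |
| 5% | 4.50 | 4.75 | 4.90 |

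The overstatement reaches 1 point when f = 0.01/p, that is 1.11%, 1.05% and 1.02% for the three values of p.

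**Worked count (p = 95%, f = 2%)**

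Of 1000 attempted patients, 980 are enrolled and 0.95 × 980 = 931 succeed. The reported rate is 931/980 = 95.0%; among attempts it is 931/1000 = 93.1%. The 980 − 931 = 49 failures after implantation are counted. The 20 placement failures are not.

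**Effect on the interval**

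The exact binomial interval in 5.3.4 does not reflect the missing patients. Take 500 attempts and about 95% success among the implanted:
- f = 2%: 466/490 = 95.1% (95% CI 92.8 to 96.8). The all-attempts rate, 466/500 = 93.2%, lies inside the interval.
- f = 5%: 451/475 = 94.9% (92.6 to 96.7). The all-attempts rate, 451/500 = 90.2%, lies below the interval.

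**The case against.** FRED is a permanent implant (2.2.2), so *treated with FRED* can naturally be read as *implanted with FRED*. On that reading every section describes one population. Section 4.1.1 also cites the regulator's requirement to register and follow patients in whom the product is implanted, and an implanted cohort suits the long-term objective. Neck coverage, apposition, perfusion and contrast retention can all fail after implantation and would still be counted. The frequency of attempts without an implant is unknown and may be close to zero. The study has no hypothesis and no acceptance criterion (5.6), and a rate labelled as applying to implanted patients would be correct as labelled.

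Much of this stands. The size is entirely assumed, the effect vanishes at f = 0, no decision rule is affected, and an implanted cohort is reasonable for long-term follow-up. The synonym reading, however, removes the wording conflict only by making the selection permanent: placement failures are then excluded by design. The regulator's text on following implanted patients does not make implantation a sound denominator for whether the device could be placed. The protocol's technical success rate also carries no label limiting it to implanted patients.

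**Conclusion.** The concern holds. The protocol words its population in two ways and does not say which applies. If implantation is a condition of entry, by 4.1 or by the meaning given to *treated*, technical success is overstated by p × f. The direction follows from the protocol's own definitions, because only failures are removed. The size does not follow from them: under the assumed 90–98% success among implanted patients it runs from nothing at f = 0% to 4.5–4.9 points at f = 5%, passing 1 point at f of about 1.0–1.1%. If *treated* is meant to include attempts and governs, there is no bias, but 4.1 and the Study Population row must then be corrected. The consequence is a biased or unlabelled descriptive rate for an indicator the protocol says the regulator requires. This should be changed.

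**What to change.** - Use one population definition in the synopsis (Study Population row and inclusion criteria), 4.1, 4.2.1, 4.2.2, 5.1 and 5.2, and state what being treated with FRED means.
- For technical success, re-sheathing performance and procedural complications, take as denominator all patients in whom FRED delivery was attempted within the window. Count those left with no FRED as technical failures and report their number.
- State the denominator for occlusion, stroke and mortality. An implanted-only population may be used if each such rate is labelled accordingly.

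The cost is wording in the sections listed and a check by sites of procedure or device-use logs, since implant registration alone will not show attempts with no implant. The protocol gives no indication of how many such attempts there are. The reported technical success rate may become slightly less favourable.
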